2.3.3 Year is missing

If only year is missing, then the year 2024 will be imputed solely for the duration calculation. The following intervals will determine OCS duration from the calculation OCS end date – OCS start date:

- 0<and<3 months: OCS dependency cannot be determined.
- >= 3 months: OCS duration is greater than or equal to 3 months.
- -12< and <-8: OCS dependency cannot be determined.
- -8<=and <=0: OCS duration was greater than or equal to 3 months.

These rules for partial dates can also be applied to determining the OCS dose relative to the screening visit.

2.4 How to deal with Overlapping OCS Dependency

There is no clearly defined rule for calculating OCS dependency for subjects who were taking multiple OCS medication that were overlapping. As a result, the following rules for overlapping medication will be followed. If a subject was taking multiple OCS medications at the same time, the duration of treatment will be:

latest stop date of the overlapping medications - earliest start date of the overlapping medications.

2.5 Last Exacerbation Partial Date

Section 3.1.6.1 of the SAP outlines definitions for both time since asthma diagnosis and time since last exacerbation but only gives imputation rules for partial dates of asthma diagnosis. Therefore, partial date rules for exacerbation dates need to be outlined. The rules are similar to diagnosis imputation:

If the day of diagnosis is missing, then this will be imputed as the 1st of the month. Missing month will be imputed as June, unless diagnosis year is the same as the year of informed consent and the informed consent date is on or before June. Then, we will impute month as the latest month in which the 1st is before the informed consent date.

Completely missing dates will not be imputed; time since diagnosis will be set to missing and reported as n (%) missing. Time since diagnosis will be summarized across patients with a complete or partial data recorded.

If the year is missing, then the time since last exacerbation will be reported as unknown.

2.6 Visit 4 Window

In sections 2.4.2 of the SAP, visit 4 is defined as Week 13 ± 5 days. There are subjects who have visit 4 outside of this window and given the small number of subjects it has been decided to be more flexible on which visits are allowed in the analysis. Although visits outside of the window will still be considered a protocol deviation we have the following classification:

- Up to five days outside of the window will be a non-important PD.
- Beyond five days outside of the window will be considered an important.

2.7 Linear Regression Model

In SAP sections 3.2.4 and 3.2.6, it states that more than just the intercept should be displayed in the final outputs however it is the intercept which is of interest and should be reported.

Linear regression models that have a population n < 10 will not be shown in the final outputs.

Throughout the linear regression sections of the SAP there is certain wording that requires more clarity. So, the following sections outline the number of model that should be used for each endpoint.

2.7.1 Secondary Endpoint 3 - Relationship Between Changes from Baseline in Airway Dynamics and Lung Functions Measurements at Week 13

The use of the word unadjusted in the SAP causes confusion over the number of models. Instead, the number of models is outlined explicitly. Three linear models will be fitted for each imaging parameter, where the endpoint will be change from baseline to week 13 in the imaging parameter:

- Model 1: Adjustment for baseline measurement of imaging parameter only
- Model 2: Adjustment for baseline measurement of imaging parameter and for change from baseline to week 13 in pre-BD FEV1
- Model 3: Adjustment for baseline measurement of imaging parameter and for change from baseline to week 13 in pre-BD FVC

CONFIDENTIAL

Developed from TP-BPM-WW-032; related to SOP-BPM-WW-001 D3250R00107

Statistical Analysis Plan Addendum

Table 4outlines the models that are expected for the analysis of tertiary endpoint 1.

Should there be no data for the assigned reference category then the most abundant category will be assigned as the reference.

Table 5 outlines all the of models expected for tertiary endpoint 2

Project Document Version No.: 3.0; Document Effective Date: 03 Sep 24 TP-GDO-WW-169-01 Effective Date: 22 Dec 21 Related to: SOP-GDO-WW-019 CONFIDENTIAL

Developed from TP-BPM-WW-032; related to SOP-BPM-WW-001 D3250R00107

Statistical Analysis Plan Addendum

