3.	To describe the relationship between changes from baseline (week 0) in airway dynamics and conventional lung function measurements at week 13, after accounting for baseline measurements of conventional lung function.	Correlation between the change from week 0 in imaging endpoints (primary and secondary FRI endpoints ^b) at week 13 and the change from week 0 in pre-BD FEV ₁ at week 13 (\pm 5 days), overall and within subgroups conditional on the baseline value of pre-BD FEV ₁ . Correlation between the change from week 0 in imaging endpoints (primary and secondary FRI endpoints ^b) at week 13 and the change from week 0 in pre-BD FVC at week 13 (\pm 5 days), overall and within subgroups conditional on the baseline value of pre-BD FVC at week 13 (\pm 5 days), overall and within subgroups conditional on the baseline value of pre-BD FVC.							

	Scatter plots of changes from week 0 in primary and secondary FRI endpoints ^b and mucus plugs score at week 13 vs. changes from week 0 in conventional lung function measures (pre-BD FEV ₁ and pre-BD FVC) at week 13. Estimated change over time (week 13 vs. week 0) in primary and secondary FRI endpoints ^{ab} , with and without adjustment for conventional lung function measures (pre-BD FEV ₁ and pre-BD FVC).
Safety	
To monitor the safety and tolerability of benralizumab.	 Safety and tolerability will be evaluated in terms of AEs, Vital signs, and Clinical laboratory. Assessments related to AEs include: Occurrence/Frequency Relationship to IP or study procedure as
	assessed by investigator
	– Intensity
	- Seriousness
	– Death
	 AEs leading to discontinuation of IP
	 Other significant AEs
	 Time to onset
	Vital signs parameters include systolic and diastolic blood pressure, and heart rate.
/ CCI	
CCI	

- a. FRI endpoints are untrimmed unless otherwise specified (Section 8.1.1.1).
- b. The primary FRI endpoint is total mucus volume at TLC; secondary FRI endpoints for evaluation under secondary objectives include total mucus plugs score at TLC, total air trapping at FRC; trimmed distal iVaww at TLC; trimmed distal siVaw at TLC and FRC; total iVlung at TLC and FRC; and total mucus plugs score at TLC.

CCI	; AE =
adverse event; CCI	; $FEV_1 = Forced$ expiratory volume in 1 second; $FRC = Functional$
residual capacity; FRI = Funct	onal Respiratory Imaging; FVC = Forced vital capacity; IP =
investigational product; iVaw	= Airway wall volume, iVlung = Lung volume, CCl
CCI ;CCI	; (CC)

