A linear regression model for imaging endpoints will be fitted, consisting of a binary explanatory variable (corresponding to week 13). The regression coefficient for time will estimate the change from baseline (week 13 vs week 0) in the imaging endpoint. The model will be fitted with and without the inclusion of the change from baseline in pre-BD FEV₁ and pre-BD FVC as individual covariates. Estimated regression coefficients for time from the unadjusted and adjusted models will be compared, to indicate whether the change from baseline in the imaging parameter is explained by changes in pre-BD FEV₁ and pre-BD FVC. Estimated regression coefficients for changes in pre-BD FVC will be reported, to quantify the average change in each imaging endpoint for every one percent increase in pre-BD FEV₁ and pre-BD FVC.

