3.2.4.3 Handling of Dropouts and Missing Data

The populations of interest do not include participants withdrawing before Week 13 and participants with one of the two measurements missing and so will not be included in the analysis.

3.2.4.4 Primary Analysis of Secondary Endpoint 3

For secondary objective 3, a scatter plot will be used to display changes from baseline at Week 13 in each imaging endpoint (including: all FRI endpoints in Table 2) against changes from baseline at Week 13 in each conventional lung function measure (including: pre-BD FEV₁ and pre-BD FVC). Both Spearman's rank and Pearson correlation coefficients will be used to describe the strength of the association between changes from baseline at Week 13 in each imaging endpoint and both of the conventional lung function measures. Estimated correlation coefficients will be reported with corresponding 95% CIs and p-values, testing the null hypothesis of no correlation.

Changes from baseline in conventional lung function measures at Week 13 may be related to baseline values. Therefore, correlation coefficients between each imaging parameter and conventional lung function measure will be reported for the overall populations and for two subgroups, based on dichotomizing at the median baseline value.

To estimate the average change from baseline (Week 13 versus Week 0) in each imaging endpoint, a linear regression model for the change from baseline in each imaging endpoint will be fitted, with adjustment for the baseline (Week 0) measurement of the imaging endpoint. The model will be fitted with and without the inclusion of the change from baseline in pre-BD FEV₁ and pre-BD FVC as individual covariates. Models including and excluding conventional lung function measures as covariates are defined below and are referred to as adjusted and unadjusted models, respectively.

The adjusted linear regression model will be as follows:

$$y_i = \beta_0 + \beta_1 x_{1i} + \beta_2 x_{2i}$$

Where:

• y_i is the change from baseline at Week 13 in the imaging endpoint
- β_0 quantifies the average change from baseline at Week 13 in the imaging endpoint after accounting for the baseline value
- x_{li} is the baseline value at Week 0 of the imaging endpoint
- β₁ quantifies the association between Y and x₁
- x_{2i} is the change from baseline at Week 13 in the conventional lung function measure
- β₂ quantifies the association between Y and x₂, after accounting for baseline measurements

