The unadjusted linear regression model will be as follows:

$$y_i = \beta_0 + \beta_1 x_{1i}$$

Where:

- y_i is the change from baseline at Week 13 in the imaging endpoint
- β₀ quantifies the average change from baseline at Week 13 in the imaging endpoint after accounting for the baseline value
- x_{li} is the baseline value at Week 0 of the imaging endpoint
- β₁ quantifies the association between Y and x₁, after accounting for baseline measurements

Two adjusted and unadjusted models will be fitted for each imaging endpoint, where the conventional lung function measure is pre-BD FEV_1 for model (i) and pre-BD FVC for model (ii).

Estimated regression coefficients for the intercept, β_0 , from the unadjusted and adjusted models will be reported with 95% CIs and p-values, and compared to indicate whether the average change from baseline in the imaging parameter is explained by changes from baseline in pre-BD FEV₁ and pre-BD FVC. Estimated regression coefficients, β_2 , for changes in pre-BD FEV₁ and pre-BD FVC will be reported with 95% CIs and p-values, to quantify the average change in each imaging endpoint for every one percent increase in pre-BD FEV₁ and pre-BD FVC.

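### Addendum 2.7 makes the intercept the reported quantity for the objective 3 regressions, so the slopes on FEV1 and FVC change promised in the protocol and SAP drop out of the outputs

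*SAP*

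**What the plan says.** **Objective.** Protocol Section 3, secondary objective 3, reads "To describe the relationship between changes from baseline (week 0) in airway dynamics and conventional lung function measurements at week 13", and goes on to require that baseline lung function be taken into account.

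**Protocol analysis text.** Section 9.4.2.2 states: "Estimated regression coefficients for changes in pre-BD FVC will be reported, to quantify the average change in each imaging endpoint for every one percent increase". The subject of that sentence names FVC only, but its closing words refer to both FEV1 and FVC.

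**SAP.** Section 3.2.4.4 regresses change in the imaging endpoint on baseline imaging (x1) and, in the adjusted model, on change in the lung-function measure (x2). It gives two coefficients distinct roles:
- β2 "quantifies the association between Y and x₂, after accounting for baseline measurements".
- β0 "quantifies the average change from baseline at Week 13 in the imaging endpoint after accounting for the baseline value".

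It undertakes to report both. Of β2 it says that these terms "for changes in pre-BD FEV₁ and pre-BD FVC will be reported with 95% CIs and p-values, to quantify the average change in each imaging endpoint". SAP Table 7 also lists regression coefficients with confidence intervals among the summaries for this endpoint.

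**Addendum.** Section 2.7 says of SAP 3.2.4 and 3.2.6: "more than just the intercept should be displayed in the final outputs however it is the intercept which is of interest and should be reported". Section 2.7.1 then keeps three models per imaging parameter. Model 1 has baseline imaging only, Model 2 adds change in FEV1, and Model 3 adds change in FVC.

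**The concern.** In Models 2 and 3 the term that relates imaging change to lung-function change is the slope β2. By the SAP's own description the intercept is an average imaging change, not an association. If Addendum 2.7 is followed as written, the models are fitted and the coefficient that speaks to the objective is left out of the tables.

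Two things are at stake. First, a reader would not learn how much an imaging endpoint changes per unit of lung-function change, nor how precisely this is estimated. Second, an estimate named in the protocol would disappear through one sentence in a list of SAP changes, without being declared as a protocol departure. The only reason given is that the intercept is the quantity of interest.

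**Working it through.** No sample-size, power or alpha figure depends on this point. The check is a comparison of texts, an algebraic question and a count.

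**1. Texts side by side**

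| Source | Intercept β0 | Slope β2 on FEV1/FVC change |
|---|---|---|
| Protocol 9.4.2.2 | Counterpart (coefficient for time) compared with and without adjustment | To be reported |
| SAP 3.2.4.4 | To be reported with CI and p-value | To be reported with CI and p-value |
| Addendum 2.7 | To be reported | Not called for; the SAP's wider display is set aside |
| Addendum 2.8.2 and 2.11.2 | Rounding rules only | Rounding rules only; they do not say which coefficients are shown |
| Addendum Section 1 (Changes from the CSP) | – | Not among its five items: analysis population, Visit 4 window, mucus plug subgroup, FRI parameters, post-hoc analysis |

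**2. Can the slope be recovered from the reported intercepts?** Write the least-squares fits as:
- Model 1: y = a1 + b1·x1
- Model 2: y = a2 + c1·x1 + β2·x2
- Auxiliary: x2 = g0 + g1·x1

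Substituting the auxiliary fit into Model 2 gives

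a1 − a2 = β2 × g0.

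Here g0 is the intercept from regressing lung-function change on baseline imaging, and it is not a planned output. Without it, the difference between the reported intercepts does not determine β2.

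This was illustrated on synthetic data with n = 29, the protocol's estimated primary analysis population. All other values were assumed.

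| Case | Fitted β2 | Model 1 intercept | Model 2 intercept | Difference |
|---|---|---|---|---|
| g0 = 0 | −0.05 | −0.1853 | −0.1853 | 0 |
| g0 = 0 | −1.05 | −0.1853 | −0.1853 | 0 |
| g0 = 0 | −2.05 | −0.1853 | −0.1853 | 0 |
| g0 ≠ 0 | −0.05 | −0.1853 | −0.183 | −0.0022 |
| g0 ≠ 0 | −1.05 | −0.2292 | −0.183 | −0.0462 |
| g0 ≠ 0 | −2.05 | −0.2732 | −0.183 | −0.0902 |

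Differences are taken before rounding. In the second case g0 = −0.0462 / −1.0506 ≈ 0.044, and the identity holds on every row. The first case shows that equal intercepts are compatible with very different slopes.

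**3. Count.** There is 1 primary FRI parameter and 7 secondary ones, so 8. Addendum 1.4 replaces two secondary parameters with two others, so the count is unchanged. With 2 lung-function measures this gives 8 × 2 = 16 slopes in the overall population. Two subgroup factors with two levels each could add up to 16 × 4 = 64, for a ceiling of 80. Addendum 2.7 suppresses regression models with n < 10, so the number of subgroup slopes cannot be fixed in advance. The tertiary endpoint 2 coefficients cannot be counted from the public text, because their covariates are redacted.

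**4. Unit of the slope.** SAP 3.2.4.4 says β2 serves "to quantify the average change in each imaging endpoint for every one percent increase in pre-BD" FEV1 and FVC, yet defines x2 only as the change in the measure and states no percent scale. A reported slope would need its unit settled.

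**The case against.** The case for leaving the Addendum alone has substance.

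- **The slope is not in the objectives table.** For objective 3, Protocol Section 3 lists correlations, scatter plots, and the estimated change over time with and without lung-function adjustment. The intercept comparison is the SAP's version of that last item, so calling the intercept the quantity of interest has a protocol basis. This stands. The commitment to the slope rests on Protocol 9.4.2.2 and SAP 3.2.4.4, but there it is explicit.
- **Association is still reported.** A reader might infer that objective 3 is left with no measure of association. It is not. SAP 3.2.4.4 keeps scatter plots and both correlation coefficients with 95% CIs and p-values, overall and split at the median baseline value. The Addendum does not touch these. They are also what Protocol 4.2 relies on when it says correlations would support clinical meaning.
- **β2 is not the term that accounts for baseline lung function.** It adjusts for baseline imaging. The baseline lung-function condition in the objective is met by the median-split correlations. This stands and limits what is lost.
- **The Addendum does not say that only the intercept is reported.** True, but it contrasts the SAP's wider display with the intercept, and no later text brings β2 back. No other reading is natural.
- **The change is openly made.** It sits under Changes to the Statistical Analysis Plan and names the SAP sections it alters. It is not disguised as a clarification; the remark about wording that needs clarity is a separate paragraph about the number of models. What stands is narrower: the change is not declared as a departure from the protocol.

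A reader might also infer that the slopes were dropped after results had been seen, because the Addendum mentions a dry run. Addendum 2.14 links the dry run only to incomplete scans. Nothing dates Section 2.7 against it or suggests that slopes were examined.

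**Conclusion.** The conflict is real and should be fixed. Followed as written, Addendum 2.7 removes from the outputs a coefficient that the protocol and SAP both say will be reported, and the departure from the protocol is not declared in Addendum Section 1. The loss is the effect size in endpoint units, adjusted for baseline imaging, with its CI and p-value. It covers 16 slopes overall, those from any subgroup models with n ≥ 10, and the corresponding coefficients for tertiary endpoint 2. Eighty is a ceiling for objective 3, not an estimate.

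The documents do not support anything larger. Sign and strength of association survive in the correlations. The primary endpoint, sample size and error rate are unaffected, the objective is descriptive, and the models are still fitted, so the slopes can be produced at any time.

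The conclusion assumes that Addendum 2.7 means the intercept in place of the other coefficients, and that the redacted 3.2.6 models follow the form of 3.2.4.4, as the SAP says they do.

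**What to change.** Amend Addendum 2.7 so that, for Models 2 and 3 and for the SAP 3.2.6 models, β2 (or the corresponding covariate coefficients) is reported with 95% CI and p-value next to the intercept. In the same sentence state the unit of the lung-function change (absolute, percent change from baseline, or percentage points of predicted), so that the coefficient matches its stated interpretation.

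If the sponsor still prefers to omit the slopes, list the omission in Addendum Section 1 as a change from the protocol and give the reason.

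The cost is a sentence or two in the Addendum and the extra columns for the slope in the affected tables. No new model is needed, because the coefficients come from models that are already fitted. If the chosen unit differs from the one programmed, the covariate has to be rescaled, or re-derived if it becomes a percent change, and the models rerun.

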3.2.1.5 Secondary Analysis of Primary Endpoint

For the secondary analysis of the primary endpoint a mixed-effects model will be employed to incorporate the repeated mucus volume measurements (corresponding to the different lobes) for each subject. The fitted model will provide estimates of the average change from baseline in mucus volume per lobe, with lobe as a fixed effect and a patient-level random effect to estimate the heterogeneity across lobes. Adjustment will be made for the baseline value of mucus volume.

Equation 1 The mixed-effects model will be as follows:

$$y_{ij} = \beta_0 + \beta_{1j}X_{ij} + \beta_2(baseline)_{ij} + b_{0j} + \varepsilon_{ij}$$

where

• y_{ij} represents change from baseline in mucus volume for subject *i* lobe *j*

- β_0 is the intercept
- β_{1j} is the coefficient for lobe *j*, estimating the average change from baseline in mucus volume for lobe *j*
- X_{ij} is an indicator of whether the mucus volume measurement for subject *i* corresponds to lobe *j*
- β_2 is the coefficient for baseline mucus volume
- $(baseline)_{ij}$ is the baseline mucus volume value for subject *i* corresponding to lobe *j*.
- b_{0i} is the random effect for the *i*th subject
- ε_{ij} is the residual error term

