1.1 Analysis Population

There is a required update to the SAP which will differ from the CSP. It related to the analysis populations in section 2.2 of the SAP. The analysis populations are taken directly form the CSP but has led to a misinterpretation which in turn has led to data being missed from the analysis which could be utilized.

The update relates to the Evaluable analysis set but impacts the Primary analysis set as well. The updated definition is outlined in Table 1.

Population/Analysis Set	Description
Evaluable	All participants who have completed three doses of study
	intervention and have baseline and post-benralizumab treatment
	study evaluation in at least one of PROs, CT scans, or spirometry
	tests – the evaluable population.

Table 1 Analysis Data Sets

The update resolves the issue that a missing PRO, for example, would lead to available spirometry tests or CT scan data not being presented. It has been clarified that only one of these need to be present to be included in the analysis set.

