2.11.3 Skewed Data

Mucus volume data that is skewed would be log-transformed according to SAP section 3.2.1. This data can be zero however, so a log plus one transformation will be used if needed. That is, each value of the data will be increased by one and then the log-transformation will be applied. The Skewness of the data is determined by checking box plots of the data and seeing if the mean deviates from the median greatly and if there is asymmetry between the quartiles.

Specific airway volume and airway wall volume are the only other FRI parameters that need to be considered for possible transformation. Should it be determined that a transformation is required the rules in SAP section 3.2.1 should be followed.

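### Objective 3 regressions: the uncentred intercept is not the average change the SAP says it is, and the addendum reports that intercept while dropping the FEV1/FVC slope

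*SAP*

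**What the plan says.** SAP 3.2.4.4 fits, for each imaging parameter,

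- unadjusted: change = b0 + b1 × (Week 0 imaging value)
- adjusted: change = b0 + b1 × (Week 0 imaging value) + b2 × (change in pre-BD FEV1 or FVC)

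It states that b0 "quantifies the average change from baseline at Week 13 in the imaging endpoint after accounting for the baseline value". The b0 estimates from the two models are to be "compared to indicate whether the average change from baseline in the imaging parameter is explained by changes from baseline in pre-BD" FEV1 and FVC. The same section requires b2 with a 95% CI and p-value, and SAP Table 7 lists regression coefficients with 95% CIs as a population-level summary.

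Protocol 9.4.2.2 describes a different model, with a binary week-13 variable: "The regression coefficient for time will estimate the change from baseline (week 13 vs week 0) in the imaging endpoint". It also commits to the slope: "Estimated regression coefficients for changes in pre-BD FVC will be reported, to quantify the average change in each imaging endpoint", in a sentence that ends by naming FEV1 as well as FVC.

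Addendum 2.7 notes that SAP 3.2.4 and 3.2.6 ask for more than the intercept, and then says "it is the intercept which is of interest and should be reported". Addendum 2.7.1 restates the analysis as Models 1 to 3 with the same covariates. Neither the SAP nor the addendum mentions centring in its visible text.

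**The concern.** There are two faults, and each makes the other worse.

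First, the label on b0 is wrong for the model as written. An intercept is the predicted outcome when every covariate is zero. In Model 1 that is a participant whose Week 0 value is zero. The label would suit the protocol's week-13 coefficient, which without covariates does equal the mean change. The SAP changed the model and kept the interpretation.

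Second, the addendum keeps the mislabelled coefficient and discards b2, the baseline-adjusted slope of imaging change on lung-function change. Objective 3 is about that relationship. The addendum files this under changes to the SAP, although it also departs from protocol 9.4.2.2.

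At stake is a table of intercepts and p-values, labelled as average changes, that can show no change when a parameter fell or a rise when nothing happened. The comparison of Model 1 with Models 2 and 3 would start from the wrong number.

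**Working it through.** **Inputs.** From the documents: the models (SAP 3.2.4.4, Addendum 2.7.1), two-sided 5% tests (SAP 3) and n = 29 (protocol synopsis). The documents give no means, SDs or scan error for the imaging parameters, so all of those below are assumptions. There is no stated figure to reproduce.

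**Identity (no assumptions).** Least squares gives

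b0 = mean(change) − b1 × mean(baseline) − b2 × mean(FEV1/FVC change).

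In Model 1, b0 equals the mean change only if b1 is zero or baseline is centred. On one simulated data set the protocol's week-13 coefficient was −0.732, equal to the mean change of −0.732; the SAP Model 1 intercept was +0.043.

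**Lung volume, raw scale, no true change.** Assume mean 5.5 L, between-participant SD 1.2 L, and independent scan error with SD e at each visit. Regression to the mean gives b1 = −e²/(1.2² + e²), so b0 = 5.5 × e²/(1.44 + e²). False-positive rates are from simulation (20,000 runs, n = 29).

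| e (L) | b0 (L) | Significant |
|---|---|---|
| 0.1 | 5.5 × 0.01/1.45 = +0.04 | 6% |
| 0.2 | 5.5 × 0.04/1.48 = +0.15 | 9% |
| 0.3 | 5.5 × 0.09/1.53 = +0.32 | 14% |
| 0.4 | 5.5 × 0.16/1.60 = +0.55 | 21% |

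Precision suffers too. The uncentred SE is larger than the centred SE by sqrt(1 + (5.5/1.2)² × 29/28) = 4.77.

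**True fall of 0.2 L, e = 0.3.** b0 = −0.20 + 0.32 = +0.12 L, the wrong sign, significant in about 6% of runs. Centred: −0.20 L, 70%.

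**Model comparison.** Assume a mean FEV1 change of 0.2 L (SD 0.25 L), an imaging change of −1.5 × FEV1 change, and e = 0.3. The mean fall is 1.5 × 0.2 = 0.30 L, wholly explained by FEV1.

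- Uncentred: Model 1 b0 = −0.30 + 0.32 = +0.02 L; Model 2 b0 = +0.02 + 0.30 = +0.32 L. An apparent rise emerges after adjustment.
- Baseline centred: −0.30 L, then 0.00 L, which is the correct reading.

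**Plug score, raw scale.** If each plug clears with probability p, the expected change is −p × baseline, so b0 = 0 whatever p is. With p of 0.3 or 0.5 and a mean of 5 to 15 plugs, the true mean change runs from −0.3 × 5 = −1.5 to −0.5 × 15 = −7.5. The intercept is significant in 2–3% of runs, against 100% centred.

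**Mucus volume halving, with variation between participants.** On the raw scale b0 is about 0 and significant in 15–17% of runs, against 95–99% centred. Log-transformation does not cure this, because log(x + 1) maps zero to zero. The intercept then recovers 3% to 63% of the true mean change as the assumed median goes from 0.1 to 20 units (units are not stated), or 4% to 22% if a fifth of participants have no mucus.

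**Which parameters can be transformed.** Addendum 2.11.3, after mucus volume, says "Specific airway volume and airway wall volume are the only other FRI parameters that need to be considered for possible transformation". Plug score, air trapping and lung volume therefore stay on the raw scale. The untrimmed distal iVaw parameters that Addendum 1.4 substitutes for siVaw are not on the list either.

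**Separate, smaller point.** In Equation 1 (SAP 3.2.1.5, reused in 3.2.2.5) the lobe coefficient is described as "estimating the average change from baseline in mucus volume for lobe" j. With an intercept and an uncentred baseline also in the model, it is not. Under reference coding it is a contrast with the reference lobe.

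**The case against.** The strongest reply concerns size. Proportional clearance forces the intercept to zero by construction. If participants instead lose a roughly constant number of plugs (Poisson mean 2 or 4, capped at baseline, mean 10 plugs), the uncentred intercept is −1.59 against a mean change of −1.84, or −2.64 against −3.44, and significant in 97% or more of runs. For lung volume, protocol 4.2 claims very low variability in FRI parameters. At a scan error of 0.1 L the bias is only +0.04 L, and a true 0.2 L fall gives −0.16 L: the right sign, though significant in 24% of runs against 100% centred. This stands. The magnitudes above are one part of a range, and with precise scans the main harm is lost precision.

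The protocol's model is no better for the comparison. The lung-function change is one value per participant, so in complete stacked data the week-13 coefficient is the same with and without it. That also stands: the SAP had good reason to change the model, and the words about accounting for baseline suggest an adjusted mean was intended. What is missing is the centring step.

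Addendum 2.7 does not literally say that only the intercept is reported, and the table shells are not available. But it sets the intercept against the SAP's request for more than the intercept, so this is the natural reading.

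Finally, the correlations with CIs, the scatter plots and the paired t-tests remain. That limits the consequence. A correlation is still neither a slope nor baseline-adjusted, and a wrong intercept would sit beside a correct mean change.

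**Conclusion.** The concern holds. That b0 is not the average change follows from least-squares algebra and rests on no assumption beyond the absence of centring in the visible text. The loss of b2 follows from the natural reading of Addendum 2.7 and departs from both SAP 3.2.4.4 and protocol 9.4.2.2.

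The size depends on unknown inputs. It ranges from a small bias with a large loss of precision to a sign reversal or a complete miss of a real fall. The primary analysis, the paired t-tests of the secondary parameters and the objective 3 correlations are untouched, and the objective is descriptive. It should be fixed, but it does not threaten the main result.

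**What to change.** In Addendum 2.7.1, state for Models 1 to 3:

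- Centre the Week 0 imaging value at its mean in the analysis population.
- Use the same participants and the same centring value in all three models. Addendum 1.1 now requires only "study evaluation in at least one of PROs, CT scans, or spirometry" tests, so a participant with CT but no spirometry could enter Model 1 and not Models 2 and 3.
- Leave the FEV1/FVC change uncentred. If it were centred as well, all three intercepts would equal the mean change and the comparison would be empty.
- Report b0 and b2, each with a 95% CI.

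Apply the same rule to the SAP 3.2.6 models where they take this form; that section is largely redacted and could not be checked. For Equation 1, report lobe least-squares means at mean baseline.

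The cost is a sentence in the addendum and one line of code per model. No new data are needed.
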